3.4	
Exclusion Criteria
 
Subjects receiving medications for chronic medical problems that may interact with elagolix, untreated hypothyroidism or hypopituitarism, known pituitary disorder, dexamethasone or CRH in the week prior to testing, use of elagolix, ketoconazole, metyrapone or mifepristone for one month prior, or known allergy to elagolix. In addition patients will be excluded if they have poorly controlled hypertension (mean systolic BP >170 mm Hg or mean diastolic BP >110 mm Hg) at screening, poorly controlled diabetes mellitus (Hemoglobin A1C >12% at screening), abnormal liver test results (total bilirubin >1.5 x upper limit normal or elevated alanine aminotransferase or aspartate amino transferase >3X upper limit normal at baseline), severe renal insufficiency (GFR <= 29 ml/min) at baseline. Patients will be excluded if they use or plan to use somatostatin analogues (octreotide, lanreotide or pasireotide) or have used these drugs within 8 months prior to study start. Patients with adrenal cortical carcinoma will also be excluded. Patients with a history of malabsorption will be excluded. Patients on HRT will be excluded.
 
Elagolix is also a substrate of CYP3A and therefore should not be used concomitantly with drugs that are strong CYP3A inhibitors including: clarithromycin, telithromycin, nefazodone, itraconazole, ketoconazole, atazanavir, darunavir, indinavir, lopinavir, nelfinavir, ritonavir, saquinavir, tipranavir.
 
Drug interactions of note (not Exclusion Criteria): Elagolix is also a substrate of CYP3A and therefore should not be used concomitantly with drugs that are strong CYP3A inhibitors including: clarithromycin, telithromycin, nefazodone, itraconazole, ketoconazole, atazanavir, darunavir, indinavir, lopinavir, nelfinavir, ritonavir, saquinavir, tipranavir. Elagolix is also a substrate of organic anion transporting polypeptide (OATP) therefore the concomitant use of strong OATP

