		
1B1 inhibitors (e.g., cyclosporine and gemfibrozil) is contraindicated as they may increase plasma concentrations of elagolix.
 
Elagolix is a weak to moderate inducer of cytochrome P450 (CYP) 3A. Co-administration with Elagolix may decrease plasma concentrations of drugs that are substrates of CYP3A (i.e. amlodipine and atorvastatin). Elagolix is a weak inhibitor of CYP 2C19. Co-administration with Elagolix may increase plasma concentrations of drugs that are substrates of CYP2C19 (e.g., omeprazole) but this only requires attention if very high doses are used such as in Zollinger-Ellison syndrome.

3.5	Study Flowchart	A study flow chart is highly recommended. It should display all clinical and laboratory measurements and the time periods (e.g., hours, days, and/or weeks) at which data are to be collected.

		
This section is a detailed explanation of the experimental design. The use of subheadings, lists, tables, or outlines are recommended. Describe the initial screening period(s), baseline period(s), treatments to be compared, study configuration (e.g., parallel, crossover, etc.), duration of the treatment period(s), control group(s), follow-up procedures, and length of time specified for washout intervals and safety follow-up.
 
This section should also include subject withdrawal criteria (e.g., terminating investigational product treatment/trial treatment) and procedures specifying:
 
 
When and not to withdraw subjects from the trial/investigational product treatment;
 
The type and timing of the data to be collected for withdrawn subjects;
 

3.6	Study Procedures	

- c) Whether and how subjects are to be replaced;
- d) The follow-up for subjects withdrawn from investigational product treatment/trial treatment.

The study will be submitted for IRB approval by the Mount Sinai Institutional Review Board and registered with the clinical trials office. A determination will be made regarding eligibility of this study for an Investigational New Drug (IND) exemption.

The following parameters will be measured:

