**Safety Monitoring and Subject Withdrawal Criteria:** Patients will be assessed at baseline, one month, three months and six months including history, physical, and laboratory testing (comprehensive metabolic panel and complete blood count with differential). Study drug will be discontinued for any adverse reactions including nausea, vomiting, and/or diarrhea, a single episode occurring within 6-8 hours after administration of Elagolix. Drug will also be discontinued for elevations greater than 3-4x normal in liver function tests, any abnormalities in electrolytes (above or below normal range) or kidney function (elevation of BUN and/or creatinine above normal range) and any abnormalities in hematologic parameters.

**Procedures for Reporting a Serious Adverse Event (SAE):** Any SAE occurring from the time of signing of the informed consent form (ICF) and for at least 30 days after the last dose of study drug must be *reported within 24 hours* to the designated safety contact and recorded on the SAE form. The investigator will supply the sponsor and the IRB/IEC with any additional requested information.

**Adverse Event Follow-up:** All adverse events will be followed until resolution, until deemed stable by the Principal Investigator, or until the patient is deemed by the Principal Investigator to be lost to follow-up.

3.7	Statistical Analysis and Sample Size Justification	
The statistical methods proposed to be used for the analysis of data should be clearly outlined, including reasons for the sample size selected, power of the study, level of significance to be used, procedures for accounting for any missing or spurious data, etc. For projects involving qualitative approaches, specify in sufficient detail how the data will be analyzed.
 
State who will be responsible for analyzing the study data (e.g., investigator, contract CRO, etc.).
 
Investigator will be responsible for analyzing the study data. The significance of the effect of elagolix treatment on different outcome measures will be assessed with the Wilcoxon matched-pairs signed rank test to generate a two-tailed p-value. Calculations will be performed with Prism 6 (Graphpad Software, Inc.).
 
Sample Size Justification: No hypothesis testing, pilot study.

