3.8	Specific Drug Supply Requirements	
The investigator is responsible for keeping accurate records of the clinical supplies, the amount dispensed to and returned by the subjects, and the disposition at the end of the study.
 
Clinical supplies must be received by a designated person at the study site, handled and stored safely and properly, and kept in a secured location to which only the investigator and designated assistants have access. Clinical supplies are dispensed in accordance with the protocol.
 
The investigator will be responsible for the destruction of the supplies at the study center pursuant to the ICH/GCP Guidelines, local regulations, and the investigator's institutional policies.
 
Elagolix 200 mg BID has an acceptable safety profile and results in rapid suppression of LH (23). We selected this dose because it has been deemed to be safe and we are aiming for maximal efficacy. Once screened and with informed consent, patients will be administered elagolix 200 mg orally twice daily for a total of 6 months.

3.9	Safety Reporting	
In addition to compliance with all FDA reporting requirements pursuant to 21 CFR 312, the Principal Investigator shall:
 
 
Report to AbbVie all serious adverse events (SAEs) experienced by a study subject receiving an AbbVie product within 24 hours of learning of the event regardless of the relationship of the event to the AbbVie product. Principal Investigator shall make available to AbbVie promptly such records as may be necessary and pertinent to investigate any such event, if specifically requested by AbbVie, and,
 
Copy AbbVie on the submission to the FDA of events meeting the definition of IND safety reports at the time of submission to the Agency; and,
 
Notify AbbVie upon any subjects receiving an AbbVie Product whose pregnancy has resulted in a negative outcome or untoward event during the course of pregnancy or upon delivery.
 

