	
s contact for reporting serious adverse drug experiences, pregnancy experiences, and communications of FDA submissions of IND safety reports shall be [contact]
 
Complaints: In addition to compliance with all FDA requirements pursuant to 21 CFR 211 and 21 CFR 820, Principal Investigator will report to AbbVie within 24 hours any suspected quality defect in an AbbVie Product or its AbbVie-provided packaging, labeling, or medical device component (collectively, "Product Complaint"). Principal Investigator will report Product Complaints that involve an AbbVie Product, whether AbbVie has supplied the AbbVie Product used in the Study or not. AbbVie's contact for reporting Product Complaints shall be [contact]
 
Collection of non-serious adverse events may be added per product-specific requirements. The events to be collected and the timing of this reporting should be included in this section as required.>
 
Patients will be evaluated and questioned to identify AEs during the study. Collection of AEs will start immediately following the signing of the informed consent forms. Illnesses present before the patient signs the consent are considered pre-existing conditions and are documented on the medical history. Adverse events that occur after the start of the study drug and up to and including 30 days after administration of the last dose of study drug will be considered treatment emergent adverse events. Any adverse events reported more than 30 days after the last dose of study drug will be considered post treatment AEs.
 
Any AEs/SAEs occurring from the time of signing the ICF and for at least 30 days after the last dose of study drug will be reported within 24 hours to the designated safety contact and recorded on the SAE form. All patients with an SAE will be followed and the outcomes will be reported. All AEs will be followed until resolution or until deemed stable by the Principal Investigator or until the patient is deemed to be lost to follow-up.
 
SAEs will be reported in accordance to FDA requirements and AbbVie will be informed on these cases.

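### The section 3.6 electrolyte, kidney and blood-count stops are judged against the normal range, not baseline, so an eligible patient with a stable old abnormality must stop elagolix for a reason unrelated to it.

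*Combined protocol and SAP*

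**What the plan says.** Section 3.6, under its safety-monitoring and withdrawal heading, sets the laboratory schedule: "Patients will be assessed at baseline, one month, three months and six months including history, physical, and laboratory testing". Drug is then stopped on several grounds. The first is clinical: "Study drug will be discontinued for any adverse reactions including nausea, vomiting, and/or diarrhea". The laboratory grounds are liver tests above 3-4 times normal, then "any abnormalities in electrolytes (above or below normal range) or kidney function (elevation of BUN and/or creatinine above normal range"), with a final ground for blood counts that is worded "and any abnormalities in hematologic parameters". The last two carry no grade, no repeat test and no reference to the patient's own starting value.

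Section 3.4 has one renal exclusion, "severe renal insufficiency (GFR" at or below 29 ml/min). It has no limit for electrolytes, BUN, creatinine or blood counts.

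Section 3.9 does recognise prior disease, but for adverse-event recording: "Illnesses present before the patient signs the consent are considered pre-existing conditions and are documented on the medical history". Section 3.8 gives the intended exposure: "patients will be administered elagolix 200 mg orally twice daily for a total of 6 months".

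On what follows a stop, the template prompt at the head of section 3.6 asks for "The type and timing of the data to be collected for withdrawn subjects". The protocol's own text answers this for adverse events only. Section 3.7 names a Wilcoxon matched-pairs signed rank test and makes the investigator responsible for the analysis. It names no analysis set and no method for missing data.

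**The concern.** A safety stop should respond to something that happens on drug. These three respond to a state that the eligibility criteria allow at entry. A woman with moderate renal impairment and a stable raised creatinine, or with mild stable anemia, can enrol and then meets the stop rule without any change. She is exposed, then taken off treatment for a reason that says nothing about elagolix. Site staff must either follow the text or deviate from it.

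In a study of 12, even one such patient matters to a description of six months of treatment. Because the analysis of stopped patients is not stated, the investigator could also decide how to handle her outcome data after seeing open-label results.

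**Working it through.** The plan gives no stop rate, power or dropout figure, so there is nothing to reproduce. The check sets entry limits against stop limits and then works out the consequences.

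**1. Entry limit against stop limit**

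| Test | Entry limit (3.4) | Stop limit (3.6) | Can an eligible, unchanged patient meet the stop? |
|---|---|---|---|
| Liver | ALT or AST above 3 × ULN, or total bilirubin above 1.5 × ULN, excluded | Above 3-4 × normal | No, for these tests |
| Kidney | GFR 29 ml/min or less excluded | BUN or creatinine above normal | Yes |
| Electrolytes | None | Any value outside normal | Yes |
| Blood counts | None | Any abnormality | Yes |

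The liver criteria are broadly aligned, although 3-4 is not a single threshold. The other three are not aligned.

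**2. Exposure lost by one such patient** (6 planned months; checks at baseline and months 1, 3 and 6)

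- Rule applied to the baseline panel: 0/6 of planned drug.
- Stop at month 1: 1/6 = 17% of planned drug; the 6-month scan falls 6 − 1 = 5 months after the last dose.
- Stop at month 3: 3/6 = 50%; the scan falls 3 months after the last dose.

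**3. How many patients.** The documents do not say. For illustration only, let p be an assumed share of eligible patients with a stable abnormality, independent across patients. The expected number of such stops is 12p, and the chance of at least one is 1 − (1 − p)^12.

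| Assumed p | 12p | Chance of at least one |
|---|---|---|
| 5% | 0.6 | 46% |
| 10% | 1.2 | 72% |
| 20% | 2.4 | 93% |
| 40% | 4.8 | 99.8% |

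The chance passes 50% at p = 1 − 0.5^(1/12) = 5.6%. No value of p has support in the documents.

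**4. Why the analysis set should be stated.** Suppose k of 12 patients stop for any reason and their outcomes are left out. Write S for the mean change in those who continue and T for the mean change in those who stop. The all-treated mean is [(12 − k)S + kT]/12, so S minus the all-treated mean is (k/12)(S − T). That is 8% of the difference S − T for k = 1, 25% for k = 3 and 50% for k = 6. Neither k nor S − T is known. If the 6-month visits are kept and all pairs are used, no pair is lost and this shift does not arise.

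**The case against.** **The rule may mean on-drug findings.** The laboratory sentence follows the one on adverse reactions and continues from it, so an investigator could take it to mean new abnormalities. That is a sensible reading, but the text does not state it and gives the normal range as the yardstick. The section 3.9 wording on prior conditions governs adverse-event recording and is not linked to the stop. Full literalness cuts another way too: the same panel is drawn at baseline, so the patient might never be dosed. The 17% figure therefore holds only if the rule is first applied at month 1.

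**Strict stopping is a fair choice.** In a 12-patient pilot in a new indication, at a dose chosen for maximal efficacy, caution is defensible. That stands as a reason to set tight limits. It does not explain admitting a patient, dosing her and stopping her for a value she arrived with. If the value is unsafe, eligibility is the place to act.

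**Stronger readings that the documents do not support.** A reader might infer that stopped patients leave the study and that their pairs are lost. Section 3.6 stops drug, not participation, and the template's own gloss on withdrawal includes ending treatment. All patients are to have the 6-month CT, and the 6-month laboratory tests and spine X-rays carry no on-drug condition. Adverse-event follow-up after a stop is specified. References in section 3.2 and the survey paragraph to six months of treatment can simply name the time point. The natural reading is that visits continue. A reader might also infer that the rule would remove a large part of the sample, but the documents give no frequency.

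**Conclusion.** The mismatch is real and follows from the text alone. Three of the four laboratory stops can be met by an eligible patient whose values have not changed, and no baseline comparison or repeat test prevents it. For a patient so affected, the loss is large: five of six months of drug if she is stopped at month 1, or all six if the rule is applied to the baseline panel. How many patients would be affected is unknown, and the illustrative shares are not evidence of frequency. Confidence is therefore high on the wording and only moderate on its practical effect.

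The gap after a stop is narrower. The 6-month assessments most naturally continue, but the plan does not say how stopped patients enter the matched-pairs analysis. This should be settled before results are seen.

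**What to change.** **Stop rule (3.6).** Define the electrolyte, kidney and hematology stops as a clinically significant worsening from baseline, confirmed on a repeat sample. The investigator should set the limits so that no eligible patient meets them at entry. The baseline panel and blood count are already scheduled, so the cost is amendment wording plus an occasional repeat sample. The downside is that mild stable abnormalities are tolerated on drug. If the investigator judges that unsafe, put the same limits into section 3.4 instead, at the price of a narrower pool of eligible patients.

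**After a stop (3.6 and 3.7).** Confirm that patients who stop drug keep the planned 6-month scan, laboratory tests, spine X-rays and surveys. Make all treated patients with available pairs the main set, and report the number of stops with reasons. Show on-drug completers only as a descriptive sensitivity analysis: they are a selected group and do not give an undiluted drug effect.

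These visits are already planned, so they add no new assessments. Keeping off-drug values in the main set can dilute the result. If patients respond equally and values off drug do not move beyond baseline, each stop lowers the mean change by between 0 (effect persists) and 1/12 = 8.3% of the on-drug effect (effect fully lost).
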